1.2 Research Question

The aim of this study is to evaluate the incidence and risk of stroke, systemic thromboembolic events, myocardial infarction, bleeding events, and mortality in relation to management of warfarin therapy among AF patients. INR target is defined as 2.0-3.0 according to current care treatment guidelines.^{9,10} The risks mentioned above are separately evaluated with different management levels of warfarin therapy. The study population is also characterized according to comorbidity, interactive medications and antiarrhythmic drugs in use. Additional study questions are related to initiation, discontinuation, and duration of warfarin treatment. The incidence of anemia and renal impairment in association with warfarin use will also be studied.

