2.3 Exploratory Objectives

- 1) To investigate and compare incidence of anemia and renal impairment among AF patients in relation to INR levels: under 2.0, 2.0-3.0, and over 3.0.
- 2) To investigate risk of stroke, systemic thromboembolic events, myocardial infarction, and bleeding events among AF patients in relation to discontinuation of warfarin treatment due to surgical operations and interventions.
- 3) To investigate how long it takes to achieve INR target in treatment initiators.
- 4) To investigate how well the INR target is maintained (TTR level).
- 5) To characterize the use of antiarrhythmic medication in AF patients at start of warfarin use and during warfarin use.
- 6) To characterize the use of medications with known interactions with warfarin in AF patients at start of warfarin use and during warfarin use.
- 7) To characterize comorbidity in AF patients using warfarin.

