3.2.2 Exclusion Criteria

- Patients with permanent residence in Finland less than 12 months prior to index date.
- Patients with age below 18 years at index date.

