3.4 Definitions of Study Variables

3.4.1 Outcomes/Endpoint Variables

The studied primary outcomes/endpoint variables of interest are defined through ICD-10 diagnosis codes (hospitalizations and deaths) or ICD-O-3 codes (cancers). See [Appendix 1](#) and [2](#) for more detail.

The time to event for each primary outcome will be calculated as the time from the index date to the time of the diagnosis of the outcome when such an event occurs during the follow-up.

Index date is defined as the date of first purchase of warfarin after 01-Jan-2007. Follow-up of the patients starts on the index date, and ends on 31-Dec-2011, at time of death or at time of emigration whichever occurs first. Treatment and comorbidity history is gathered from the period 01-Jan-2005 to 31-Dec-2006.

Primary outcomes:

- Stroke
- Other systemic thromboembolic events excluding stroke
- Myocardial infarction
- Bleeding events
- Mortality all-cause
- Mortality (stroke)
- Mortality (myocardial infarction)
- Mortality (systemic thromboembolic events excluding stroke)
- Mortality (bleeding events)

The studied secondary outcomes/endpoint variables of interest are anemia and renal impairment.

Time to anemia is defined as the time from index date to time of first decrement of 20 g/L in haemoglobin or time when haemoglobin is under the reference value.

Time to renal impairment is defined as the time from index date to time when creatinine is under the reference value.

Secondary outcomes

- Anemia
- Renal impairment

In the statistical analysis follow-up for each time to event outcome continues until the time of the event, death, emigration or 31-Dec-2011 whichever comes first.

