APPENDIX 2 ICT NUMBERS AND REFERENCE VALUES FOR LABORATORY PARAMETERS

The ICT numbers for the laboratory variables with the reference values valid in adults in Finland in 2013

Test name	Test abbreviation	ICT number (HUS)		Lower target	Upper target	Unit
International Normalized Ratio	P-INR	4520		2.0	3.0	
Blood picture	B-PVKT	2474				
	B-PVK+TKD	2475				
	B-PVK+Ne	8370				
Hemoglobin	B-Hb	1552	women	117	155	g/L
			men	134	167	g/L
Hematocrit	B-HCT		women	35	46	%
			men	39	50	%
Leukocyte count	fB-Leuk			3.4	8.2	E9/L
erythrocyte count	B-Eryt		women	3.90	5.20	E12/L
			men	4.25	5.70	E12/L
mean corpuscular haemoglobin	E-MCH			27	33	pg/cell
mean corpuscular volume	E-MCV			82	98	fL
platelet count	B-Trom			150	360	E9/L
Creatinine	P-Crea	4600	women	50	90	μmol/L
			men	60	100	μmol/L
Alanine aminotransferase	P-ALAT	1024	women	10	45	U/L
			men	10	70	U/L

Source: Laboratory of Helsinki University Central Hospital. Available at: http://huslab.fi/cgi-bin/ohjekirja/tt_show.exe?assay=2475&terms=pvk. Accessed February 25, 2013.

Note: The ICT numbers may not be the ones mentioned above if the laboratory is using some data system other than Hospital District of Helsinki and Uusimaa (HUS).

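### Anemia is counted from the index date with no normal haemoglobin required at entry, so patients already anemic are scored as incident cases at their first test

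*Protocol*

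**What the plan says.** The target is stated twice as incidence. Protocol section 1.2 says "The incidence of anemia and renal impairment in association with warfarin use will also be studied", and exploratory objective 1 in section 2.3 reads "To investigate and compare incidence of anemia and renal impairment among AF patients in relation to INR levels".

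Section 3.4.1 fixes the anemia endpoint. The event is either a first drop of 20 g/L, which is one branch, or an absolute threshold, which the text words as "or time when haemoglobin is under the reference value". Both branches are timed from the index date. Follow-up ends at the event, death, emigration or 31-Dec-2011. Appendix 2, headed as "reference values valid in adults in Finland in 2013", gives the lower haemoglobin limits as 117 g/L (women) and 134 g/L (men).

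Section 3.2.2 has two exclusions: "Patients with permanent residence in Finland less than 12 months prior to index date" and "Patients with age below 18 years at index date". The history period in section 3.4.1 covers treatment and comorbidity in 2005-2006. Neither section 3.4.3 nor Appendix 4 lists anemia as a comorbidity. Section 4.1.3 plans stratified rates and Cox models for anemia and states no at-risk condition.

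**The concern.** An incidence rate counts first occurrences among people who are free of the condition at entry. The threshold branch does not ask whether the low value is new. A man who has been steady at 125 g/L for years is below 134 g/L and has an event at his first blood count after index, although nothing has happened to him. The rate then mixes baseline prevalence with incidence. Because existing cases are picked up early, they load the first months of follow-up.

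At stake are the absolute anemia rates, overall and by INR and TTR stratum. The comparison between INR levels may also suffer, because existing cases are credited to whatever INR level holds at the first test.

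**Working it through.** **Text check.** I looked for any rule that would keep a patient with an already low haemoglobin out of the numerator.

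| Protocol section | Content | Removes existing anemia? |
|---|---|---|
| 3.2.2 | Exclusion on residence and age | No |
| 3.4.1 | Clock from index; threshold met by any low value | No |
| 3.4.1 | History of treatment and comorbidity | No haemoglobin named |
| 3.4.3 | Haemoglobin 20 g/L fall and under-reference value, among covariates | No; no time point given |
| 4.1.3, objective 1 | Rates and Cox models for anemia | No at-risk condition |
| Appendix 4 | Comorbidity list | Anemia not listed |

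The 20 g/L branch differs. It needs a fall, so stable anemia does not trigger it. The value from which the fall is measured is not stated, however.

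**Illustration of size.** The protocol has no figure to reproduce here.

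Inputs from the protocol: 32 000 patients and a mean follow-up of 3 years (section 4.2).

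Assumed inputs, not in the protocol: share already below the limit p = 0.10 to 0.30 (3 200 to 9 600 of 32 000); true incidence i = 0.05 to 0.10 per person-year; first test t = 0.1 year after index; every existing case is tested. Over a window of T years:

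- events per patient = p + (1 − p)(1 − exp(−iT))
- person-years per patient = t·p + (1 − p)(1 − exp(−iT))/i
- apparent rate = events / person-years

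Low end, p = 0.10, i = 0.10, T = 3: events 0.100 + 0.90 × 0.2592 = 0.333; person-years 0.010 + 0.2333/0.10 = 2.343; rate 14.2 per 100 person-years, 1.4 times the true 10.

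High end, p = 0.30, i = 0.05, T = 3: events 0.300 + 0.70 × 0.1393 = 0.3975; person-years 0.030 + 0.0975/0.05 = 1.980; rate 20.1, 4.0 times the true 5.

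| p | i per 100 PY | Year 1 rate (ratio) | 3-year rate (ratio) | Existing cases as share of events, year 1 / 3 years |
|---|---|---|---|---|
| 0.10 | 10 | 21.4 (2.1) | 14.2 (1.4) | 54% / 30% |
| 0.10 | 5 | 16.2 (3.2) | 9.0 (1.8) | 70% / 44% |
| 0.20 | 10 | 35.3 (3.5) | 19.5 (1.9) | 72% / 49% |
| 0.20 | 5 | 29.9 (6.0) | 13.8 (2.8) | 84% / 64% |
| 0.30 | 10 | 52.7 (5.3) | 26.1 (2.6) | 82% / 62% |
| 0.30 | 5 | 46.9 (9.4) | 20.1 (4.0) | 90% / 75% |

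**Sensitivity to the assumptions.** With a later first test (0.25 year), the same p and i = 3 to 10 per 100 person-years, the 3-year ratio runs from 1.4 (p = 0.10, i = 10) to 5.8 (p = 0.30, i = 3). The upper end rises because the assumed true incidence is lower.

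**Direction.** Existing cases who are tested contribute events at a rate of 1/t. Even if the first test came only at 3 years, that is 1/3, or 33 per 100 person-years, still above the assumed 5 to 10. Within these assumptions the rate bias is always upward.

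**The case against.** **The SAP can add the restriction.** Section 4.1 defers detail to a separate SAP, which is not shown, and an at-risk rule could appear there. But the protocol itself fixes the event, the time origin and the end of follow-up, and as fixed they do not measure incidence. Section 3.3 also says data are requested on the basis of the protocol, and no pre-index haemoglobin window is named. If those values are not requested, a SAP cannot restore the baseline.

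**Low haemoglobin is already a covariate.** Section 3.4.3 lists it, and the rates and models use the other covariates. The entry repeats the outcome definition without a time point. Even as a baseline covariate it would not take existing cases out of the overall numerator.

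**A spurious link with low INR.** A reader might infer that new users are first tested while INR is still under 2.0, so that existing anemia creates a false association with low INR. The documents give no timing of blood counts, and the argument does not reach prevalent users. A Cox model on time since index compares patients at the same time since index, so early clustering goes largely into the baseline hazard. Crude stratum rates, or a model pooling new and prevalent users, could still be biased.

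**Renal impairment.** A reader might extend the point to patients with raised creatinine. The text does not support that: "Time to renal impairment is defined as the time from index date to time when creatinine is under the reference value", with lower limits of 50 and 60 μmol/L in Appendix 2. Read literally, a patient whose creatinine is already high is not counted at all. Section 4.1.3 also gives no rate or model for renal impairment. The direction of that definition is a separate error.

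**Weight.** The outcome is exploratory in section 2.3, although section 3.4.1 calls it secondary. The primary objectives are untouched. This stands.

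**Conclusion.** The point holds for anemia. As written, the threshold branch counts existing anemia as incident, and the rates asked for in section 2.3 will be too high. That conclusion needs only that some patients are below the limit at index and are tested afterwards.

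The size rests on assumed prevalence, incidence and test timing. About 1.4 to 4.0 times over three years is the fairer summary, since section 4.2 assumes three years of mean follow-up; 2.1 to 9.4 times describes the first year alone. Distortion of the INR comparison is possible, mainly in the crude rates, but its size and direction are not established. The change is worth making but is not critical, because the outcome is exploratory.

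**What to change.** In section 3.4.1:

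1. Admit to the risk set for the under-reference branch only patients whose last haemoglobin at or before index is at or above the Appendix 2 lower limit.
2. Let patients already below the limit have an event only by the 20 g/L fall, measured from that last pre-index value, and report them separately.
3. Let patients with no pre-index value enter by delayed entry at their first normal value, with a sensitivity analysis that leaves them out.

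In section 3.3, request haemoglobin values from a stated window before each patient's index date.

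Once the direction of the creatinine definition has been reconciled, apply the same at-risk rule to renal impairment.

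The cost is a few sentences, a somewhat wider laboratory request and a smaller risk set. Delayed entry has its own price: among patients without a baseline value, a true early drop before the first test is lost, and leaving these patients out does not recover it. The sensitivity analysis shows only whether the result depends on this group.

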4.1.3 Exploratory Objectives

Objective 1: Stratified incidence rates with 95% CIs will be estimated for anemia as endpoint within the strata of the exposure variables (INR levels and TTR categories) and other covariates.

The crude and adjusted hazard ratio (HR) estimates with 95% CIs and P-values will be estimated separately within the INR levels and TTR categories using the conventional Cox's proportional hazards model adjusting for other covariates. For INR the category 2.0–3.0 will be used as the reference category. Similarly for TTR the category $\geq 60\%$ of time will be used as the reference category.

Objective 2: Discontinuity period of warfarin treatment due to a surgical operation or intervention is identified as starting two weeks before and ending two weeks after such procedure.

Stratified incidence rates with 95% CIs will be estimated for stroke, systemic thromboembolic events, myocardial infarction, and bleeding events in the strata of other covariates within periods of warfarin discontinuity. Also, an indicator variable of the discontinuity period will be added to the Cox's proportional hazards model.

Sensitivity analysis will be done to study the robustness of the discontinuity period definition.

Objective 3: The distribution of days taken to achieve INR target in the new warfarin user population will be provided. Stable INR-target is considered achieved after 3 consecutive INR measurements are within the target 2.0-3.0.

Objective 4: For the new warfarin user population the distribution of TTR at 1, 6, and 12 months after start of warfarin treatment stratified by other covariates. For the prevalent warfarin user population the distribution of TTR at the end of 2010 and 2011 stratified by other covariates.

Objective 5: Warfarin users will be tabulated by use of antiarrhythmic medication (yes/no) at start of follow-up and during follow-up. During follow-up users will also be stratified by the INR and the TTR levels.

Objective 6: Warfarin users will be tabulated by use of interaction medication (yes/no) at start of follow-up and during follow-up. During follow-up users will also be stratified by the INR and the TTR levels.

Objective 7: Warfarin users will be tabulated by comorbidities.

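### Renal impairment is defined by creatinine below the reference value, so a raised creatinine never triggers the event, and the analysis of its objective names only anemia

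*Protocol*

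**What the plan says.** Protocol Section 3.4.1 lists anemia and renal impairment as secondary outcomes and gives each a time-to-event rule. For renal impairment: "Time to renal impairment is defined as the time from index date to time when creatinine is under the reference value". The sentence just before it sets the anemia event as the "time of first decrement of 20 g/L in haemoglobin or time when haemoglobin is under the reference value".

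Appendix 2 is introduced as "The ICT numbers for the laboratory variables with the reference values valid in adults in Finland in 2013". Its creatinine rows read "women 50 90 μmol/L" and "men 60 100 μmol/L", with the lower limit first and the upper limit second. The haemoglobin row for women reads "women 117 155 g/L"; the lower limit for men is 134 g/L.

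The objective served is the first one in Section 2.3: "To investigate and compare incidence of anemia and renal impairment among AF patients in relation to INR levels". Section 1.2 also announces that both conditions will be studied. The matching analysis in Section 4.1.3, Objective 1, begins: "Stratified incidence rates with 95% CIs will be estimated for anemia as endpoint". Neither that paragraph nor the Cox model paragraph after it mentions renal impairment.

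**The concern.** An endpoint called renal impairment should become positive when renal function gets worse, and on this marker that means a rise. The rule looks for a fall. It repeats the phrase used for haemoglobin in the sentence before, where a fall is the right direction, so a copying slip is the likely origin.

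A programmer who follows the protocol would build a variable that flags low or normal creatinine and label it renal impairment. Incidence rates and hazard ratios by INR level from that variable would not address the objective. The omission in Section 4.1.3 adds a second gap: the objective promises a comparison for two conditions, and the analysis text delivers it for one.

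**Working it through.** The protocol states no event count, incidence or power for renal impairment or anemia, so there is no figure to reproduce. The check applies the written rule to the protocol's own limits.

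**Inputs.** Rule: the event occurs when creatinine is under the reference value (Section 3.4.1). Limits L to U: 50 to 90 μmol/L for women, 60 to 100 μmol/L for men (Appendix 2). The creatinine values c in the table are illustrations chosen for this check.

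**Readings compared.** Section 3.4.1 does not say which limit is meant, so both are tried: (A) event if c < L; (B) event if c < U. The reversed rule is (C) event if c > U.

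| Sex | c (μmol/L) | A: c < L | B: c < U | C: c > U |
|---|---|---|---|---|
| Women | 45 | event | event | no |
| Women | 70 | no | event | no |
| Women | 100 | no | no | event |
| Women | 200 | no | no | event |
| Women | 500 | no | no | event |
| Men | 55 | event | event | no |
| Men | 80 | no | event | no |
| Men | 110 | no | no | event |
| Men | 200 | no | no | event |
| Men | 500 | no | no | event |

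Under A, only values below the range count. Under B, values inside the range count too. Under both, every value above the range is a non-event. Only C counts raised values.

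**Is it corrected elsewhere?** Appendix 1 has a row for anemia that points to Appendix 2, but no row for renal impairment. Section 3.4.3 describes laboratory parameters for anemia only. Appendix 2 supplies limits but no event rule. The sentence in Section 3.4.1 is therefore the only definition.

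**Objective against analysis.** Section 2.3, Objective 1: anemia and renal impairment. Section 4.1.3, Objective 1: anemia. The two do not match.

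**Patients abnormal at index.** Section 3.2.2 excludes only on residence and age. The follow-up rule in Section 3.4.1 sets no condition on laboratory status at index and names no starting value for the 20 g/L fall. Read literally, a woman at 110 g/L before index and still at 110 g/L at her first later test (110 < 117) would be an event without any change. The same question would arise for creatinine once its direction is corrected. How many patients this touches cannot be computed, because no baseline haemoglobin or creatinine distribution is given.

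**Reach.** Table 4.2-1 uses incidence rates of 1.5, 3 and 6 per 100 patient years, chosen from published rates for stroke and systemic embolism, bleeding and death. It does not depend on this definition.

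**The case against.** The strongest reply is about weight. Section 3.4.1 calls the outcome secondary, but it serves only an exploratory objective. No primary objective or power figure uses it. The study is a retrospective register study, so correcting the definition before analysis loses no creatinine data and affects no patient. Since Section 4.1.3 names no renal analysis, the wrong rule currently feeds no stated result. All of this stands and limits the scope. It does not make the definition right: the protocol fixes the rule itself, so an analysis plan that reversed it would contradict the protocol, and Section 6.4 requires revisions to be documented as amendments.

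A reader might infer three stronger things that the document does not support.

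- That the endpoint misses every renally impaired patient. The event is met by any qualifying value during up to five years of follow-up, so an impaired patient with one low value (or, if the upper limit is meant, one value under 90 or 100 μmol/L) would be counted. What can be said is that a raised value never triggers the event.
- That the protocol sets the trigger at the lower limit. It says only the reference value, and the limit is left open.
- That the protocol counts existing anemia as new, and that this dominates the hazard ratios. The text is silent on patients abnormal at index, and Section 4.1 commits to a separate statistical analysis plan that could restrict the risk set. Any count would need an assumed baseline prevalence with no anchor in the protocol.

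**Conclusion.** The renal impairment definition is wrong as written. Under either reading of the Appendix 2 limits a raised creatinine is a non-event, while low values, or low and normal values, are events. This rests on the quoted sentence, the printed limits and the fact that creatinine rises as renal function falls. Separately, renal impairment is named in Exploratory Objective 1 and absent from its analysis.

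The number of patients misclassified cannot be given from the protocol. The consequence is confined to one exploratory objective, but for the renal half of it a variable built to the written rule cannot answer the question. Handling of patients already abnormal at index is a clarification worth making in the same amendment, not a demonstrated error.

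**What to change.** In Section 3.4.1, define the renal event as the first creatinine above the sex-specific upper reference limit in Appendix 2 (above 90 μmol/L for women, above 100 μmol/L for men). In Section 4.1.3, Objective 1, name renal impairment next to anemia for both the incidence rates and the Cox models. A matching row in Appendix 1 would keep the endpoint list complete.

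In the same amendment, state that patients who already meet a laboratory criterion at index are not counted as incident cases for that endpoint, or are reported separately, and say which haemoglobin value the 20 g/L fall is measured from, where pre-index values are available.

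Reversing the direction and naming the endpoint costs a few words. The baseline clarification may cost more. The history period in Section 3.1 covers treatment and comorbidity, and Table 3.3-1 lists laboratory values without giving their period, so it is not clear that pre-index haemoglobin and creatinine will be obtained. The data request may need to be widened, and patients without a usable baseline value would need a stated rule or would drop out of these exploratory analyses.

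### Renal impairment is dated by creatinine falling below the reference value, so a rise in creatinine can never count as the event

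*Protocol*

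**What the plan says.** The protocol treats renal impairment as an outcome in its own right. Section 3.4.1 states: "The studied secondary outcomes/endpoint variables of interest are anemia and renal impairment". Section 2.3, Exploratory Objective 1, gives its purpose: "To investigate and compare incidence of anemia and renal impairment among AF patients in relation to INR levels". Section 1.2 also lists it among the study questions.

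The definition is one sentence in Section 3.4.1: "Time to renal impairment is defined as the time from index date to time when creatinine is under the reference value". Just before it, anemia is dated at the "time of first decrement of 20 g/L in haemoglobin or time when haemoglobin is under the reference value".

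Appendix 2 supplies the reference limits. Its creatinine row begins "Creatinine P-Crea 4600 women 50 90" and continues with 60 and 100 for men, in µmol/L. Each sex therefore has a lower and an upper limit.

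**The concern.** Plasma creatinine is a marker that goes up as kidney function goes down. A rule that dates renal impairment at a low value selects the wrong patients. It records an event for someone whose creatinine is low for another reason, such as small muscle mass, and records nothing for someone whose creatinine climbs.

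At stake is any rate, time to event or hazard ratio by INR level produced under the name of renal impairment. Such results would describe low creatinine. A reader of the study report would take them as findings on kidney function, and nothing in the output would reveal the inversion.

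**Working it through.** The protocol gives no rate, power or sample size for this endpoint, so there is no figure to reproduce. The check applies the rule to the protocol's own limits and then looks for any text that corrects it.

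**Inputs**
- Rule (Section 3.4.1): event when creatinine is below the reference value.
- Limits (Appendix 2): women 50 to 90 µmol/L, men 60 to 100 µmol/L.

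**Possible readings of the rule.** The sentence does not say which limit is the reference value.
- Reading A, lower limit: event if creatinine < 50 (women) or < 60 (men).
- Reading B, upper limit: event if creatinine < 90 (women) or < 100 (men).
- Reversed direction, for comparison: event if creatinine > 90 (women) or > 100 (men).

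**Illustrative patients** (values chosen for this check)

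| Creatinine, µmol/L | Reading A | Reading B | Reversed |
|---|---|---|---|
| Woman at 45 | event (45 < 50) | event (45 < 90) | no event |
| Woman rising from 80 to 200 | no event | event, but at 80 | event at 200 |
| Man at 55 | event (55 < 60) | event (55 < 100) | no event |
| Man at 80 | no event | event (80 < 100) | no event |
| Man at 250 | no event | no event | event (250 > 100) |

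Reading A is the natural one, because it matches how the same phrase works for haemoglobin. It misclassifies four of the five patients. Reading B is worse in kind: it also counts values inside the normal range, and it dates the rising woman's event at her normal value. Under neither reading can a value above the upper limit trigger the event.

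**Does other text correct it?**
- Appendix 1 has a row for anemia that points to Appendix 2, but no row for renal impairment.
- Section 3.4.3 lists laboratory parameters for anemia only.
- Section 4.1.3, Objective 1, describes the analysis for anemia only: "Stratified incidence rates with 95% CIs will be estimated for anemia as endpoint within the strata of the exposure variables". It offers no other renal definition.
- Appendix 2 gives the limits but says nothing about direction.

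The sentence in Section 3.4.1 is therefore the sole definition. The anemia sentence before it uses the same phrase about the reference value, and there the direction is right. A carry-over from that sentence is the likely origin, though this is an inference and the conclusion does not depend on it.

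**The case against.** The strongest case on the other side accepts the error and disputes its weight.

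- **Reach.** Renal impairment serves only an exploratory objective. It is not an outcome in the primary or secondary objectives, it does not enter the power table, and it is not a listed covariate, so it cannot distort the adjusted hazard ratios elsewhere. This stands.
- **No renal analysis to spoil.** Section 4.1.3, Objective 1, plans rates and hazard ratios for anemia and does not mention renal impairment. This stands as a description of that section, but it is a second gap rather than a defence. Section 2.3 still promises incidence compared across INR levels, and Section 3.4.1 still names the outcome.
- **The analysis plan could put it right.** Section 4.1 says a separate plan will be written before any analysis, and the data are retrospective, so nothing would be lost. That argument works for missing detail. Here the protocol fixes a rule, and Section 6.4 requires the study to follow the protocol and revisions to be documented as amendments. A plan that quietly reversed the direction would contradict the protocol.
- **Some worsening patients are still counted.** A patient whose function declines could also have a low value at some time and so be recorded. This is true, but the record would not reflect the decline, and its date would be unrelated to it.
- **A first value above the limit is a crude endpoint.** It would include patients already above the limit at the index date, and single transient rises. This is a fair point about detail that the analysis plan can settle. It does not argue for keeping the inverted rule.

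**Conclusion.** The definition is wrong as written and has to be changed before the outcome is analysed. Under either reading of the reference value, no creatinine above 90 µmol/L in women or 100 µmol/L in men can be an event. Under the natural reading, the events are exactly the values below 50 and 60 µmol/L. The renal half of Exploratory Objective 1 cannot be answered with this endpoint. The anemia half and all primary and secondary objectives are unaffected.

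The conclusion rests on one fact from outside the protocol, that creatinine rises as kidney function falls, and on the limits in Appendix 2. How many patients would be misclassified cannot be derived, because the protocol gives no creatinine distribution for this cohort. The direction of any resulting bias in the INR comparison is likewise unknown.

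**What to change.** 1. **Section 3.4.1:** replace the sentence by one that defines time to renal impairment as the time from the index date to the first creatinine above the upper reference value in Appendix 2, that is, above 90 µmol/L in women and above 100 µmol/L in men.
2. **Appendix 1:** add a row for renal impairment with a pointer to Appendix 2, as already done for anemia.
3. **Section 4.1.3, Objective 1:** name renal impairment beside anemia, so that the methods cover what Section 2.3 promises.
4. **Analysis plan:** state how patients already above the limit at the index date are handled, and whether a single raised value is enough.

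The cost is three short edits recorded as a protocol amendment. Creatinine is already among the laboratory parameters in Appendix 2, so no further variable is required, and the sample size text does not change.
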